2.3 BENEFIT/RISK ASSESSMENT

The benefit/risk assessment is dependent on the combination administered and will be described in the cohort appendix for each respective combination (eg, Appendix Cohort A, Appendix Cohort B, etc.).

3 OBJECTIVES AND ENDPOINTS

The study objectives and endpoints are listed in [Table 2](#).

Table 2: Objectives and Corresponding Endpoints

Objectives	Endpoints
Primary	

 To determine the safety of each immunotherapy combination in participants with mCRPC. 	
 Incidence and severity of AEs.
Secondary	
 ORR: A composite endpoint where response is defined as a participant meeting at least one of the following: 
 CTC response: Change from unfavorable (≥ 5 cells/7.5 mL of blood) to favorable (≤ 4 cells/7.5 mL of blood). Participants with a baseline CTC value < 5 cells/7.5 mL of blood will not be evaluated for this criterion. PSA response: Confirmed PSA response is defined as $\geq 50\%$ reduction in PSA from baseline, with a repeat assessment confirming the result at least 3 weeks later. Participants without a baseline and at least 2 post-baseline PSA assessments will not be evaluated for this criterion. Confirmed response of CR or PR by objective radiographic disease assessment using modified RECIST version 1.1 (ie, CR or PR and no progression in bone per the PCWG3; Scher et al., 2016). Per RECIST, to be assigned a best overall response of CR or PR, changes in tumor measurements must be confirmed by repeat assessments that should be performed no less than 4 weeks after the criteria for response are first met. Participants who received at least 1 dose of the combination study intervention or component

	
of the combination but do not have RECIST assessment for any reason will be counted as not responding.
 
 • DCR at 9 months: Defined as CR, PR, or SD for 9 months as best response by PCWG3-modified RECIST 1.1. Participants who received at least 1 dose of the study intervention combination or component of the combination but do not have RECIST assessment for any reason will be counted as not responding. • rPFS: Defined as time from initiation of study intervention to the first objective evidence of radiographic progression, or death due to any cause (whichever occurs first). • OS: Defined as the time from initiation of study intervention until death due to any cause. • OS rate at 12 months.
Exploratory	
 • To evaluate tumor and immune biomarkers and their association with treatment outcome (antitumor activity and/or safety). • To evaluate the PK of the components of the immunotherapy combination. • To evaluate the immunogenicity (ADA) of the components of the immunotherapy combination. 
 • Association of tumor and immune biomarkers from tissue, blood, and/or stool with clinical outcomes, including ORR, DCR, rPFS, and tolerability. Biomarkers to be studied will be chosen based on the immunotherapy combination. • Molecular characterization of CTC and evaluation of percent change from baseline. • Enumeration of CTC ≥ 1 at baseline with conversion to CTC0 on treatment. • PSA: 
 ◦ Percent change in PSA from baseline at 12 weeks. ◦ Maximum change in PSA at any point after initiation of study intervention. ◦ Time to PSA progression defined as the time from study treatment initiation to the date that a $\geq 25\%$ increase and absolute increase of ≥ 2 ng/mL above the nadir (or baseline value for participants who did not have a decline in PSA) in PSA. The increase must be confirmed by a second consecutive assessment conducted at least 3 weeks later. • Sparse PK analysis. • Presence of ADA against biologic components of each immunotherapy combination.

ADA = anti-drug antibodies; AE(s) = adverse event(s); CR = complete response; CTC = circulating tumor cells; CTC0 = a measure of zero CTC; DCR = disease control rate; ECOG = Eastern Cooperative Oncology Group; mCRPC = metastatic castration-resistant prostate cancer; ORR = objective response rate; OS = overall survival; PCWG3 = Prostate Cancer Clinical Trials Working Group 3; PK = pharmacokinetics; PR = partial response; PSA = prostate-specific antigen; RECIST = Response Evaluation Criteria in Solid Tumors; rPFS = radiographic progression-free survival; SD = stable disease

4

STUDY DESIGN

4.1 OVERALL DESIGN

This is an open-label, non-randomized, exploratory platform study designed to assess the safety and antitumor activity of multiple immunotherapy combinations in participants with mCRPC who have received prior therapy. The platform study will consist of 2 stages: Stage 1, an initial stage to evaluate safety, biomarkers, and clinical activity of the combination and Stage 2, an expanded cohort, when warranted, based on the safety, clinical activity, and/or biomarker results from Stage 1. The Sponsor intends to modify and/or add new combinations to the protocol as data emerge from this and other trials.

This study will be conducted in participants with histologically-confirmed mCRPC that is measurable or non-measurable by Prostate Cancer Clinical Trials Working Group 3 (PCWG3)-modified Response Evaluation Criteria in Solid Tumors (RECIST) 1.1. Participants with brain metastases are excluded unless treated and stable by imaging for at least 4 weeks prior to the first dose of study intervention. Participants must have received prior secondary androgen receptor signaling inhibitor therapy (eg, abiraterone, enzalutamide, apalutamide) and may have received prior chemotherapy for mCRPC. Participants must consent to baseline and on-treatment biopsies, if medically feasible. A minimum of 7 participants in each cohort must have a non-bone metastatic lesion that can be biopsied. Participants must have adequate organ and hematologic function and acceptable performance status.

After consenting to participate in this clinical trial, participants will be screened for enrollment. If they meet all inclusion criteria and do not meet exclusion criteria, they will be referred for a pre-treatment biopsy of a metastatic lesion. Participants must also provide consent for archival tissue from a prior biopsy or surgery for prostate cancer. Each participant will be assigned per the Investigator's discretion to receive one of the enrolling combination study interventions.

Participants will be monitored for safety and efficacy. An on-treatment biopsy is required when medically feasible, ideally after the second dose of the immunotherapy combination. An optional biopsy may be obtained at the time of disease progression, including from participants who respond and subsequently progress. The on-treatment biopsies should be taken from the same lesion as the pre-treatment biopsy when feasible.

Approximately 15 participants, including a minimum of 7 with a non-bone metastatic lesion that can be biopsied, will be enrolled in each immunotherapy combination cohort in Stage 1. Enrollment of participants in each cohort may occur simultaneously. An additional approximately 15 participants, including a minimum of 7 with a non-bone metastatic lesion, will be enrolled in Stage 2, if the cohort is expanded.

The duration of immunotherapy combination study intervention will be dependent on the combination administered and will continue for the duration described in the cohort appendix for each respective combination, unless the participant is no longer clinically benefiting (as evidenced by symptomatic or radiographic disease progression and/or clinical deterioration); experiences any toxicity meeting specified discontinuation criteria (as described in the cohort appendix for each respective combination) or unacceptable toxicity in the best clinical discretion of the treating physician; reaches the maximum duration of study intervention; or withdraws consent. Participants will be followed for up to 2.5 years from the time of the initiation of study intervention. Depending on the combination administered, participants who are clinically benefiting, as defined by the Investigator at the end of the study treatment period, may have post-study access to the immunotherapy combination received during the study after agreement from the Medical Monitor.

4.2 SCIENTIFIC RATIONALE FOR STUDY DESIGN

The scientific rationale for this study is provided in [Section 2](#). The scientific rationale for the individual cohorts will be provided in the cohort appendix for each respective combination.

4.3 JUSTIFICATION FOR DOSE

The dose and schedule selected will be described in the cohort appendix for each respective combination (eg, Appendix Cohort A, Appendix Cohort B, etc.). The duration of immunotherapy combination study intervention will be dependent on the combination administered.

4.4 TREATMENT BEYOND DISEASE PROGRESSION

Accumulating evidence indicates that a minority of patients treated with immunotherapy may derive clinical benefit from continued treatment despite initial evidence of disease progression ([Wolchok et al., 2009](#)). The PCWG3 introduced the concept of treatment beyond progression (where clinical benefit by one or more disease manifestations is being observed) as clinical measure for outcome in prostate cancer ([Scher et al., 2016](#)). The PCWG3 recommendation included a reporting metric of no longer clinically benefiting (NLCB), defined as the date and specific reason(s) therapy was ultimately discontinued, to allow individualized provider-patient decisions to discontinue or continue treatment.

Therefore, participants receiving immunotherapy combinations in this study will be permitted to continue study intervention beyond initial Investigator-assessed disease progression (according to PCWG3-modified RECIST 1.1) provided all of the following criteria are met:

- Absence of symptoms and signs indicating rapid disease progression, including decline in performance status, and confirmation of disease status required

- Absence of progressive tumor at critical anatomical sites (eg, cord compression) requiring urgent alternative medical intervention
- Participant is adequately consented regarding the potential risks of continuation of ineffective therapy/failure to initiate effective alternative therapy, if any
- Written agreement from the Medical Monitor.

The assessment of clinical benefit should consider whether the participant is clinically deteriorating and unlikely to receive further benefit from continued treatment.

All decisions to continue treatment beyond initial progression must be discussed with the Medical Monitor and written agreement from the Medical Monitor should be documented in the study records.

Participants should discontinue study intervention upon evidence of further progression, defined as an additional $\geq 10\%$ increase in tumor burden from the time of initial progression (including all target lesions and new measurable lesions, or unequivocal progression of non-target lesions).

New lesions are considered measurable at the time of initial progression if the diameters are ≥ 10 mm (except for pathological lymph nodes, which must have a short axis of ≥ 15 mm). Any new lesion considered non-measurable at the time of initial progression may become measurable and therefore included in the tumor burden measurement if the diameter increases to ≥ 10 mm (except for pathological lymph nodes, which must have an increase in short axis to ≥ 15 mm).

4.5 END OF STUDY DEFINITION

The end of this study is defined as the date when the last visit of the last participant occurs or the date at which the last data point required for statistical analysis or safety follow-up is received from the last participant, whichever occurs later.

The total length of each study cohort, from screening of the first participant to the end of the cohort, will depend on the study intervention administered and will be described in the cohort appendix for each respective combination.

5 STUDY POPULATION

This study will enroll participants with mCRPC. Eligibility criteria are provided in the cohort appendix for each respective combination (eg, Appendix Cohort A, Appendix Cohort B, etc.).

5.1 INCLUSION CRITERIA

Inclusion criteria are provided in the cohort appendix for each respective combination.

5.2 EXCLUSION CRITERIA

Exclusion criteria are provided in the cohort appendix for each respective combination.

5.3 LIFESTYLE CONSIDERATIONS

Lifestyle considerations or restrictions, if required, will be provided in the cohort appendix for each respective combination (eg, Appendix Cohort A, Appendix Cohort B, etc.).

5.4 SCREEN FAILURES

Screen failures are defined as participants who consent to participate in the clinical study but are not subsequently enrolled in the study. A minimal set of screen failure information is required to ensure transparent reporting of screen failure participants to meet the Consolidated Standards of Reporting Trials (CONSORT) publishing requirements and to respond to queries from regulatory authorities. Minimal information includes demography, screen failure details, eligibility criteria, and any serious adverse event (SAE).

Individuals who do not meet the criteria for participation in this study (screen failure) may be rescreened.

6 STUDY INTERVENTION

Study intervention is defined as any investigational intervention(s), marketed product(s) or placebo intended to be administered to a study participant according to the study protocol.

6.1 STUDY INTERVENTION(S) ADMINISTERED

The dose and schedule selected will be described in the cohort appendix for each respective combination (eg, Appendix Cohort A, Appendix Cohort B, etc.). The duration of immunotherapy combination study intervention will be dependent on the combination administered.

Administration of study intervention will be performed in a monitored setting in which there is immediate access to trained personnel and adequate equipment and medicine to manage potentially serious reactions.

6.2 PREPARATION/HANDLING/STORAGE/ACCOUNTABILITY

The Investigator or designee must confirm that appropriate temperature conditions have been maintained during transit for all study intervention received and any discrepancies are reported and resolved before use of the study intervention.

Only participants enrolled in the study may receive study intervention and only authorized site staff may dispense and/or administer study intervention. All study intervention must be stored in a secure, environmentally controlled, and monitored (manual or automated) area in accordance

with the labeled storage conditions with access limited to the Investigator and authorized site staff.

The Investigator, institution, or the head of the medical institution (where applicable) is responsible for study intervention accountability, reconciliation, and record maintenance (ie, receipt, reconciliation, and final disposition records).

Further guidance and information for the final disposition of unused study interventions are provided in the Pharmacy Manuals.

6.3 RANDOMIZATION AND BLINDING

6.3.1 Intervention Assignment

This is not a randomized study. Assignment to one of the immunotherapy combinations will be made by the Investigator using his/her best clinical discretion based on the participant's medical history and disease status and knowledge of the available immunotherapy combinations open for enrollment.

6.3.2 Blinding

This is an open-label trial; therefore, the Sponsor, Investigator, and participant will know the study intervention administered.

6.4 STUDY INTERVENTION COMPLIANCE

Study intervention compliance will be described in the cohort appendix for each respective combination as compliance measures will be dependent on how the immunotherapy combination is administered.

6.5 CONCOMITANT THERAPY

Any medication or vaccine (including over-the-counter [OTC] or prescription medicines, vitamins, and/or herbal supplements) that the participant is receiving at the time of enrollment or receives during the study must be recorded along with:

- Reason for use
- Dates of administration including start and end dates (or indicated as ongoing, as applicable)
- Dosage information including dose, route of administration, and frequency

The Medical Monitor should be contacted if there are any questions regarding concomitant or prior therapy.

6.5.1 Permitted Therapy

Concomitant medications or treatments (eg, acetaminophen/paracetamol, diphenhydramine) may be prescribed if considered necessary for adequate prophylactic or supportive care except for those medications identified as “excluded” in [Section 6.5.2](#) or in the cohort appendix for each respective combination (for combination-specific excluded medications).

All concomitant medication will be recorded on the electronic case report form (eCRF), including all prescription, OTC and intravenous (IV) medications and fluids. If changes occur during the trial period, documentation of drug dosage, frequency, route, and date should also be included on the eCRF.

All concomitant medications received within 28 days prior to the first dose of study intervention and 100 days after the last dose of study intervention should be recorded. Concomitant medications administered after 100 days after the last dose of study intervention should be recorded for SAEs and adverse events of special interest (AESIs) (as applicable and as defined in the cohort appendix for each respective combination).

6.5.2 Prohibited Therapy

The medications listed below are prohibited during the study. The Sponsor must be notified if a participant receives any of these during the study.

- Any concurrent systemic chemotherapy, immunotherapy, biologic, hormonal treatment or radiotherapy (except palliative radiotherapy) not specified in this protocol or subsequent amendments. Concurrent use of hormones for noncancer-related conditions are permitted.
 - Exception: Androgen deprivation therapy. Participants are required to maintain castrate-level testosterone (< 50 ng/dL) with a gonadotropin-releasing hormone (GnRH) agonist or antagonist ± antiandrogen. Participants without history of bilateral orchiectomy are required to remain on ADT.
- Any concurrent investigational anticancer therapy not specified in this protocol or subsequent amendments.
- Anti-CTLA-4, anti-PD-L1, or anti-PD-1 agents through 100 days after the last dose of study intervention, except for agents that are not part of the immunotherapy combinations.
- Immunosuppressive medications at chronic systemic doses > 10 mg/day prednisone (or equivalent) within 28 days before the first dose (note: hormone replacement therapy (HRT), such as thyroxine, insulin, or physiologic corticosteroid replacement therapy ≤ 10 mg of prednisone/day for adrenal or pituitary insufficiency, etc. is not considered a form of systemic treatment). A temporary course of steroids (ie, contrast allergy, chronic

obstructive pulmonary disease) may be permitted, depending on the duration and dose, after discussion and agreement with the Medical Monitor.

- Live attenuated vaccines within 30 days prior to the first dose of study intervention and through 180 days after the last dose of study intervention. Examples of live vaccines include, but are not limited to, the following: measles, mumps, rubella, varicella/zoster, yellow fever, rabies, bacille Calmette-Guerin (BCG), and typhoid vaccine.
- Any botanical preparation (eg herbal supplements or traditional Chinese medicines) intended to treat the disease under study. Use of marijuana and its derivatives for treatment of symptoms related to cancer or to cancer treatment are permitted.

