1.3 SCHEDULE OF ACTIVITIES

The Schedule of Activities (SOA) shown in [Table 1](#) provides a general overview of the types and timing of the tests and procedures that will be performed in this study. The combination-specific tests and procedures, as well as the timing, will be described in the cohort appendix for each respective combination and will supersede the general overview provided here.

Table 1: Schedule of Activities

Tests & Procedures	Screening/ Enrollment ^a	On-Treatment: Immunotherapy Combination Treatment					End of Treatment ^b	Follow up	
		Cycle 1	Cycle 2	Cycle 3	Cycle 4	Cycle 5 Onward			
Day		To be determined based on immunotherapy combination Refer to the cohort appendix for each respective combination for details on combination-specific timing							14 - 28 days after last dose
Window (days)	-28		± 3	± 3	± 3	± 3	± 7	± 10	± 14
Informed consent ^d	X								
Review of I/E criteria	X								
Medical and cancer history	X								
Physical examination	X	X	X	X	X	X	X		
ECOG performance status	X	X	X	X	X	X	X	X	
Vital signs (see Section 8.2.3)	X	X	X	X	X	X	X		
Body weight ^e	X			X		X (every 3 cycles)	X		
Hematology (see Table 4)	X	X ^f	X ^f	X ^f	X ^f	X ^f	X	X	
Clinical chemistry (see Table 4)	X	X ^f	X ^f	X ^f	X ^f	X ^f	X	X	
Urinalysis	X						X		
Prostate-specific antigen	X	X	X	X	X	X	X	X	
Testosterone level	X								
12-lead ECG ^g	X		X		X				
Circulating tumor cells ^h		X ^f	X ^f	X ^f	X ^f	X ^f	X		
cfDNA (blood) ⁱ	X		X ^f		X ^f		X		
Circulating soluble analytes/PK/ADA ^j	X	X ^f	X ^f	X ^f	X ^f		X		
Blood immune biomarkers ^j	X	X ^f	X ^f	X ^f	X ^f		X		
Archival tumor tissue	X								

Tests & Procedures	Screening/ Enrollment ^a	On-Treatment: Immunotherapy Combination Treatment					End of Treatment ^b	Follow up	
		Cycle 1	Cycle 2	Cycle 3	Cycle 4	Cycle 5 Onward			
Day		To be determined based on immunotherapy combination Refer to the cohort appendix for each respective combination for details on combination-specific timing						14 - 28 days after last dose	110 days after last dose
Window (days)	-28		± 3	± 3	± 3	± 3	± 7	± 10	± 14
Tumor biopsy ^k	X		X				X (at PD [optional]) ^k		
Stool collection ^l	X		X						
Concomitant medications	X	X	X	X	X	X	X	X	
Adverse events	All AEs/AESIs/SAEs will be collected for at least 100 days after the last dose of study intervention ^m								
Immunotherapy combination administration ⁿ		Refer to the cohort appendix for each respective combination for details on study intervention administration							

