7 DISCONTINUATIONS OF STUDY INTERVENTION AND PARTICIPANT DISCONTINUATION/WITHDRAWAL

7.1 DISCONTINUATION OF STUDY INTERVENTION

Participants must discontinue study intervention if they experience any of the following:

- Intolerable toxicity related to study intervention, including the development of an adverse event (AE) determined by the Investigator to be unacceptable even with the participant's potential response to intervention due to the severity of the event
- Any medical condition that may jeopardize participant safety if he continues to receive the study intervention
- Use of another anticancer therapy (see [Section 6.5.2](#) and as described in the cohort appendix for each respective combination, as applicable)
- Symptomatic deterioration attributed to disease progression

- Progression of disease: Either unequivocal symptomatic progression necessitating a change in therapy in the opinion of the treating physician or confirmed radiographic progression as defined by cross-sectional imaging per PCWG3-modified RECIST 1.1 (see [Appendix 3](#)) in the absence of clinical benefit (refer to [Section 4.4](#)).

Participants have the right to voluntarily withdraw from study intervention at any time for any reason. In addition, the Investigator has the right to withdraw a participant from study intervention at any time. Reasons for withdrawal from the study intervention may include, but are not limited to, the following:

- Investigator or Sponsor determines it is in the best interest of the participant
- Participant noncompliance

The primary reason for study intervention discontinuation should be documented on the appropriate eCRF page.

The visit at which disease assessment shows progressive disease (PD) may be used as the treatment discontinuation visit if it occurs within 28 (± 7) days after the last dose of study intervention. Participants who discontinue study intervention for any reason other than PD or loss of clinical benefit should have an end of treatment discontinuation assessment as outlined in the SOA (see [Section 1.3](#)). All participants should continue follow-up as outlined in the SOA.

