5.4.2.1 Composite Response Rate

CRR is a composite endpoint where response is defined as a participant meeting at least one of the following:

- CTC response: Change from unfavorable (≥ 5 cells/7.5 mL of blood) to favorable (≤ 4 cells/7.5 mL of blood). Participants with a missing baseline CTC value or baseline CTC value < 5 cells/7.5 mL of blood will not be evaluated for this criterion. The baseline CTC value is defined as the last available value recorded prior to the first administration of study intervention.
- PSA response: Confirmed PSA response is defined as $\geq 50\%$ reduction in PSA from baseline, with a repeat assessment confirming the result at least 3 weeks later. Participants without a PSA value at baseline will not be evaluable for this criterion. The baseline PSA value is defined as the last available value recorded prior to the first administration of study intervention.
- Objective radiographic response (ORR): Best overall response of CR or PR by objective radiographic disease assessment of soft-tissue, non-bone lesions, as determined by PCWG3-modified RECIST version 1.1. Per RECIST, to be assigned a best overall response of CR or PR, changes in tumor measurements must be confirmed by a repeat radiographic assessment performed no less than 4 weeks after the criteria for initial radiographic response were first met. In addition, responders must not have bone lesions that have progressed, as determined by PCWG3 criteria. Participants with measurable disease at baseline who received at least 1 dose of any component of the combination study intervention but do not have evaluable RECIST assessments for any reason will be counted as not responding. Participants without measurable, soft-tissue disease at baseline will not be evaluable for this criterion.

Response rates will be estimated within each cohort and 95% CIs will be estimated using the Clopper-Pearson method. Response rates and 95% CIs will also be presented for each individual criterion of CRR (CTC response, PSA response, and ORR).

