5.7.1 Cohort Expansion Rules

A Simon two-stage minimax design (Simon, 1989) will be implemented for each cohort. In Stage 1, 15 participants will be enrolled. If there are 2 or more responses in these 15 participants, 15 additional participants may be enrolled in Stage 2 for a total of 30 participants in the cohort. For the purposes of cohort expansion, CRR will be used to determine response (ie, CTC response, PSA response, or objective radiographic response).

In addition to efficacy criteria stated above, safety data will also be assessed when determining whether to expand a cohort. If there are ≥ 6 participants meeting cohort-specific toxicity criteria requiring permanent treatment discontinuation, an ad hoc SAC meeting will be held to further review all safety data and provide input on assessing the benefit-risk profile. The SAC will

provide a recommendation in regard to expansion to Stage 2, continuation or discontinuation of the cohort. This ad hoc review will be in addition to the ongoing safety monitoring performed by the SAC, who may recommend terminating a combination cohort at any time for safety reasons. The threshold of 6 participants was chosen because this translates to a posterior probability of 0.69 that the true toxicity rate is > 30%, assuming 15 participants are enrolled per cohort and a minimally informative beta (0.5, 2.5) prior.

If the cohort has an acceptable safety profile but has not demonstrated at least 2 responses, no additional participants will be enrolled into the cohort. However, this decision may be revisited if follow-up translational analysis or emerging external data identifies a subset of participants most likely to derive benefit from the combination therapy that was underrepresented in the cohort. Under this scenario, any modifications to the study design of the combination, including justification for participant selection or enrichment, will be detailed in an amendment to the appropriate cohort appendix.

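### SAP 5.4.2.1 has no rule for PSA values taken after a change in anticancer or antiandrogen therapy, so on the core documents a PSA fall that follows such a change counts in the 2/15 and 6/30 decisions

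*Protocol*

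**What the plan says.** **What is permitted.** Protocol 6.5.2 prohibits concurrent "hormonal treatment or radiotherapy (except palliative radiotherapy) not specified in this protocol or subsequent amendments". Androgen deprivation is the stated exception: "Participants are required to maintain castrate-level testosterone (< 50 ng/dL) with a gonadotropin-releasing hormone (GnRH) agonist or antagonist ± antiandrogen". It adds: "Participants without history of bilateral orchiectomy are required to remain on ADT". The section does not separate an antiandrogen ongoing at baseline from one started, stopped or switched after first dose. Protocol 7.1 lists "Use of another anticancer therapy" among the reasons study intervention must stop, and refers back to 6.5.2.

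**What counts as a PSA response.** SAP 5.4.2.1 requires at least a 50% "reduction in PSA from baseline, with a repeat assessment confirming the result at least 3 weeks later". Only participants with no baseline PSA are non-evaluable. Nothing is said about PSA values after a change of therapy.

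**What the response drives.** Meeting any one of the three criteria makes a CRR responder. SAP 5.7.1 states: "For the purposes of cohort expansion, CRR will be used to determine response (ie, CTC response, PSA response, or objective radiographic response". Two responders in 15 allow Stage 2. Six in 30 make the combination worthy of further investigation (SAP 3.3).

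**What the SAP does elsewhere.**
- rPFS (5.4.2.3) and duration of response (5.4.3.4) are censored at a tumor assessment before subsequent anticancer treatment.
- Time to PSA progression (5.4.3.3) is censored, for those without progression, at the last PSA before subsequent anticancer therapy.

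**The concern.** The composite is the efficacy endpoint that opens Stage 2 and supports the final call, yet its PSA component lacks the therapy-change rule given to three less decisive endpoints. If a participant's antiandrogen changes after first dose, or subsequent anticancer therapy begins, a later PSA fall may reflect that change as well as the immunotherapy. As written, the whole fall is credited to the combination. With thresholds as low as 2 of 15 and 6 of 30, one or two such responders could alter either decision.

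**Working it through.** **Step 1: does the text count such a fall?** Take a participant with a baseline PSA whose antiandrogen is switched after first dose and whose PSA then halves, confirmed at least 3 weeks later.
- Protocol 6.5.2: the switch is neither clearly allowed nor clearly barred.
- SAP 5.4.2.1: the participant is evaluable, and both PSA values qualify.
- SAP 5.7.1 and 3.3: the participant is a responder for 2/15 and 6/30.

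The same follows for PSA values after subsequent anticancer therapy. Protocol Table 1 schedules PSA at end of treatment and into follow-up, and PSA response is not limited to on-treatment values.

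**Step 2: reproduce the stated design.** Inputs from SAP 3.3: Stage 1 n = 15, continue on 2 or more; total n = 30, success on 6 or more; null rate 10%, alternative 25%.
- Early termination at p = 0.10: 0.9^15 + 15 × 0.1 × 0.9^14 = 0.2059 + 0.3432 = 0.549 (stated 55%). P(expand) = 1 − 0.549 = 0.451.
- Success: the sum over x from 2 to 15 of P(X1 = x) × P(X2 ≥ max(0, 6 − x)), where X1 and X2 are both binomial(15, p). This gives 0.068 at p = 0.10 (stated 0.07) and 0.774 at p = 0.25 (stated 77%).

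All three stated figures reproduce.

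**Step 3: sensitivity to false responders.** Assumption: k Stage 1 participants are certain false responders, and everyone else responds at 10%. For k = 1, expansion needs at least 1 of the other 14: 1 − 0.9^14 = 1 − 0.2288 = 0.771. Success is the sum over x from 1 to 14 of P(Y = x) × P(X2 ≥ max(0, 5 − x)), with Y binomial(14, 0.10), which gives 0.156.

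| False Stage 1 responders | P(expand) | P(6 or more of 30) |
|---|---|---|
| 0 | 0.451 | 0.068 |
| 1 | 0.771 | 0.156 |
| 2 | 1.000 | 0.305 |

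The 1.000 holds by construction, because the threshold is 2.

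**Step 4: the same question as a rate.** Assume a fraction q of true non-responders has a confirmed PSA fall from a therapy change. The apparent null rate is then 1 − 0.9 × (1 − q).

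| q | Apparent rate | P(expand) | P(6 or more of 30) |
|---|---|---|---|
| 0 | 0.100 | 45.1% | 6.8% |
| 2% | 0.118 | 54.3% | 12.7% |
| 5% | 0.145 | 66.2% | 24.8% |
| 10% | 0.190 | 80.8% | 49.5% |

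Neither k nor q is given in the documents. Both ranges are assumed.

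**The case against.** **Existing controls.** The antiandrogen wording is an exception inside a ban. Its verbs concern continuity, and 7.1 stops study intervention if another anticancer therapy is used. Read together, these fit continued background therapy better than free switching. That narrows the point but does not remove it: the core text never says so expressly, and stopping study intervention does not take later PSA values out of the response definition.

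**Cohort appendices.** Eligibility and combination-specific excluded medications are in appendices that were not supplied, and SAP appendices may modify the methods by cohort. This stands. The claim is limited to the core protocol and SAP.

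**No evidence of frequency.** Participants are castration-resistant and have already had a secondary androgen receptor signaling inhibitor. Nothing shows that antiandrogen changes occur on study or that they halve PSA in this population. The figures would be the same for any cause of misclassification. This stands, so they are illustrative only.

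**Decisions are not mechanical.** The SAP says Stage 2 may open, subject to safety. It reports each criterion separately and disclaims type I error control. This softens the consequence, but the plan still quotes error rates for these thresholds, and those rates depend on what counts as a response.

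**A stronger reading the documents do not support.** Table 1 marks "Testosterone level" at screening only, and a reader might infer that this is why a hormonally driven fall is counted. It is not. SAP 5.4.2.1 uses PSA values alone, so more testosterone tests would change nothing. Moreover, the combination-specific schedule "will be described in the cohort appendix for each respective combination and will supersede the general overview provided here". Nor do the documents support reading 6.5.2 as permitting hormonal changes in general, or extending the point to the CTC criterion.

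**Conclusion.** The point holds in limited form. In the core documents, PSA response has no rule for values obtained after a change in anticancer or antiandrogen therapy. Protocol 6.5.2 leaves on-study antiandrogen changes unaddressed. A confirmed fall after such a change would count in both decisions. The gap lies in the response definition and is inconsistent with the SAP's own handling of rPFS, duration of response and time to PSA progression.

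The size is unknown. If one of the 15 Stage 1 participants were a false responder at a true CRR of 10%, expansion would rise from 45% to 77% and the final false-positive rate from 0.068 to 0.156. With none, nothing changes. The conclusion assumes that no cohort appendix closes the gap. If one does, a cross-reference in the SAP is enough.

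**What to change.** - **SAP 5.4.2.1.** State that PSA values obtained after the start of subsequent anticancer therapy, or after an antiandrogen is started, stopped or switched following first dose, do not count toward PSA response. Keep the participant in the CRR denominator. Name the antiandrogen change explicitly, because the SAP's existing rules refer to subsequent anticancer therapy and do not say whether such a change is included.
- **SAP 3.3 and 5.7.1.** Report the 2/15 and 6/30 counts with and without this rule.
- **Protocol 6.5.2 and the SAP.** Reconcile the two so that sites and the analysis read the antiandrogen exception the same way. No position is taken here on which antiandrogen use should be allowed.

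**Cost.** SAP wording and one derived flag. Protocol 6.5 already requires start and end dates for concomitant medication, and Table 1 collects alternate anticancer therapy in follow-up. The downside is that a genuine PSA response after an incidental change is left out of the main figure. The count without the rule keeps it visible.
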